# **Chapter**

## **Methodology**

### 2.1. Study design

[figure not shown]
This was a double-blind randomized controlled trial; both assessors and patients were blinded to group allocation. Figure 1 illustrates the overall study design. The study was registered in the clinical trial system at registry.gov (reference number: NCT 02490371).

### 2.2. Participant recruitment

#### 2.2.1 Inclusion and exclusion criteria

A convenient sampling method was adopted. Patients who were diagnosed with their first-ever stroke and referred to the Physiotherapy Department at Queen Elizabeth Hospital for post-stroke rehabilitation between November 2015 to December 2016 were screened for eligibility by an independent physiotherapist using criteria shown in Table 1.

**Figure 1: Experimental design and patient flow**

**Table 1. Inclusion and exclusion criteria**

Inclusion criteria:	Exclusion criteria:

1. First episode of stroke;

2. Aged 60 or more;

3. Muscle strength of grade <5 and >2 based on manual muscle testing of the hand or fingers on the paretic side;

4. Time since stroke onset > 1 month and < 6 months;

	

1. Mini Mental State Test score ≤ 24;

2. Mental illness;

3. Contra-indications to rTMS according to guidelines formulated by Wassermann (e.g., intracranial implants, epilepsy, cardiac pacemaker, implanted medication pumps);

4. Unstable cardio-pulmonary condition.

#### 2.2.2. Sample size estimation

The sample size was estimated from previously published data on one of the primary outcome measures, the motor-evoked potential (MEP). In a study involving a sample of 20 people by Takeuchi et al. (Takeuchi et al. 2008), a significant improvement in MEP was shown in the intervention group. The estimated effect size was about 0.6. Based on this, with the power set at 90% and  $p < 0.05$ , the minimum estimated sample size would be 22. When considering a 10% attrition rate, the minimum sample size required would be 24 individuals with stroke.

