#### 2.4.2 Experimental group

The participants in the experimental group underwent transcranial magnetic stimulation over hotspot at contralesional M1 region on weekdays over a 2-week period (i.e., 10 sessions), using a Magstim Rapid Stimulator (Magstim Company, Whitland, UK). We used a figure-of-eight coil (each loop 70 mm in diameter) for delivering the stimulation. The stimulation protocol of rTMS used was at a low frequency of 1 Hz with a stimulus intensity of 90% of rMT for a total of 1200 pulses in each session. This low-frequency protocol was adopted because the stimulation parameters were shown to result in down-regulation of motor cortical excitability over the contralesional cortex (Boggio et al., 2006). For frequencies from 0.2 to 1 Hz (low frequency), which favor the manifestation of the long-lasting inhibitory phase, may lead to cortical inhibition. Conversely, frequencies >2 Hz can mask the inhibitory phase of the preceding pulse,

thereby maintaining the neurons in a state of excitation (Moliadze et al. 2003). A meta-analysis by Zhang et al. (2017) found that low frequency rTMS was more beneficial than high frequency rTMS, and that rTMS administered to the contralesional hemisphere elicited better improvements in upper limb motor recovery than when applied to the lesioned hemisphere (Zhang et al., 2017).

The participants in the experimental group also underwent structured upper limb exercise training conducted by a registered physiotherapist in Queen Elizabeth Hospital. Each participant exercised at his or her own pace and was encouraged to perform the exercise continuously for thirty minutes in each session. In the treatment sessions during the first 2 weeks, the participants performed the 30-minute exercise training immediately after the brain stimulation. For the subsequent 10 weeks, the participants continued to receive exercise training twice per week. In each exercise session, two modes of exercises with 15 minutes for each were offered to improve task performance and dexterity of the paretic upper limb. The specific exercises included: 1. reach and grasp exercises: stacking cones or placing cones, and 2. fine motor control exercises of the hand .

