**Figure 6: Measurement schedule**

## 2.6 Outcome measures

A battery of assessment tools was chosen to evaluate the participants across the domains of International Classification of Function, Disability, and Health endorsed by the World Health Organization (i.e., body functions/structures, activity and participation WHO Disability Assessment Schedule (WHO 2010). The upper-extremity portion of the Fugl-Meyer Motor Assessment Scale (FMA) (Fugl-Meyer et al., 1975) was the primary behavioral measure outcome of arm function, whereas the motor evoked potential (MEP) was the primary physiological measure. Secondary measures included grip force (Takeuchi et al., 2008), the Action Research Arm Test (ARAT), the Nine Hole Pegboard test (NHPT), the Box and Block test, the reaction time test, and the Stroke Impact Scale (SIS).

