### 2.6.1. Measures of body structures/function

#### 2.6.1.1 *Fugl-Meyer assessment (FMA)*

In the upper-extremity portion of the Fugl-Meyer Motor Assessment Scale (FMA) (Appendix VIII), 25 test items included measurement of movement, coordination, and reflex action of the different parts of the paretic upper extremity. The score could range

from 0 to 66. Better motor function was reflected by a higher FMA score (Fugl et al., 1975). The FMA scores have been shown to have high construct validity, test-retest and interrater reliability (Platz et al., 2005). The minimum clinically important difference MCID of FMA was 5.2 points for the upper extremity portion (Wagner et al., 2008).

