#### *2.6.1.2 Motor evoked potential (MEP)*

To obtain the MEP of the FDI, EMG activity was measured using silver–silver chloride (Ag-AgCl) electrodes placed on the skin overlying the FDI. The peak-to-peak MEP amplitude was recorded, which reflects cortical excitability (Malcolm et al., 2007) (Figure 7). Ten averaged MEPs evoked from the M1 hotspot on both the ipsilesional and contralateral sides at 120% rMT were recorded using the Magstim 200 (Magstim Company, Whitland, UK). If the EMG could not be triggered at 100% of the resting motor threshold, the MEP was defined as “cannot be triggered” and set at zero.

If the MEP was absent when stimulating the lesioned hemisphere by the stroke, the motor hotspot was defined as being symmetrical to the contra-lesional hemisphere. The signal was amplified, bandpass filtered (1-5k Hz), and digitized for off-line analysis with ADC sampling rate of 3kHz by a built-in EMG device in Brainsight 2 (Brainsight 2, Rogue Research Inc., Montreal, Canada).

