## 2.8. Statistical analysis

The software package SPSS 21.0 for Windows (IBM, Armonk, NY, USA) was used for statistical analysis. The demographic characteristics of the participants and outcome variables at baseline were compared using the Chi-square test (for nominal data), Mann-Whitney U test (for ordinal data), and independent t-test (for continuous

data). Next, for each continuous outcome measure (FMA, MEP, GS, ARAT, B&B, RT), a  $2 \times 3$  two-way repeated measures ANOVA (mixed design; within-subject factor: time; between-subject factor: group) was used to determine whether there was a significant treatment effect on each of the outcome variables (i.e., significant group  $\times$  time interaction effect). If any substantial difference was found in particular baseline characteristics between the two groups, the variables would be entered as covariates in the above ANOVA model. Post-hoc analysis was then performed to examine the within-group changes over time using paired t-tests and between-group differences in change score at week 2 and week 12 using independent t-tests.

For analysis of the NHPT, because the failure cases were assigned a value of 600s, non-parametric statistics was used. Friedman test and post-hoc Wilcoxon test were used to examine the within-group changes over time, while Mann-Whitney U test was used to examine the difference between the two groups at week 2 and 12.

Next, for those clinical outcome variables that yielded a significant treatment effect (i.e., significant group  $\times$  time interaction effect), Pearson's product moment correlation coefficients were used to determine the degree of correlation between changes in these variables and those in MEP on both sides.

Intention to treat analysis was first conducted. Any missing data would be substituted using the last-observation-carried-forward (LOCF) method. This was followed by on-protocol analysis, in which only those participants who completed all outcome assessments were included.

The alpha was set at 0.05, except for post-hoc tests where the alpha was adjusted to 0.025 (i.e., Bonferroni correction) because of the 2 comparisons made (within-group analysis: baseline Vs week 2; week 2 Vs week 12; between-group comparison of change score: week 2 and week 12).

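### Does the 22/24 sample size need reworking because it rests on an undefined MEP effect size and gives no power for FMA?

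*Combined protocol and SAP*

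**What the plan says.** Section 2.2.2 states the basis of the calculation: "The sample size was estimated from previously published data on one of the primary outcome measures, the motor-evoked potential (MEP"). The source is a study of 20 people in which "a significant improvement in MEP was shown in the intervention group. The estimated effect size was about 0.6". With 90% power and p < 0.05 the section arrives at 22 patients, raised to 24 for 10% attrition. It names no hemisphere, time point, type of effect size, contrast or test.

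Section 2.6 sets up two primary outcomes: FMA "was the primary behavioral measure outcome of arm function, whereas the motor evoked potential (MEP) was the primary physiological measure". Section 2.6.1.1 adds for FMA that "The minimum clinically important difference MCID of FMA was 5.2 points for the upper extremity portion", but no section gives FMA an SD, a target difference or a power figure.

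Section 2.6.1.2 defines the trial's MEP variable as peak-to-peak amplitude and records it on two sides: "Ten averaged MEPs evoked from the M1 hotspot on both the ipsilesional and contralateral sides". Section 2.4.2 explains the choice of stimulation by its "down-regulation of motor cortical excitability over the contralesional cortex". Section 2.8 tests FMA and MEP alike with a "two-way repeated measures ANOVA (mixed design; within-subject factor: time; between-subject factor: group"), at alpha 0.05, and reads the treatment effect from the group-by-time interaction.

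**The concern.** Two things catch the eye.

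First, the 0.6 cannot be traced. MEP is recorded on both hemispheres, and the treatment is meant to lower excitability on the contralesional one, so an improvement could be a rise on one side or a fall on the other. The source result is described within the intervention group, whereas this trial tests a between-group interaction. If 0.6 were a within-group standardised change or a two-group standardised difference, 22 patients would fall short of 90% power, in the second case by a wide margin.

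Second, FMA is a primary outcome with a quoted clinically important difference, and nothing says what difference 24 patients could detect. If FMA power were low, a non-significant interaction could mean either no effect or too few patients.

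**Working it through.** **Inputs.** From section 2.2.2: effect size 0.6, power 90%, alpha 0.05, N = 22 then 24, attrition 10%. From section 2.3: 1:1 allocation. From section 2.8: two groups, three time points, interaction test. From section 2.6.1.1: 5.2 points for FMA. Assumed, because not stated: two-sided tests, the correlations over time shown below, and the SD of FMA change.

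**1. Can 22 be reproduced?** Power is from the noncentral F or t distribution.

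| Reading of 0.6 | Calculation | Result |
|---|---|---|
| Cohen's f from partial eta-squared, interaction | λ = f²·2(N−2) = 0.36 × 2 × 20 = 14.4; df 2, 40 | 91.5% at 22 (89.9% at 21) |
| f = 0.6, between-group effect, correlation 0.5 | λ = f²·3N/(1+2ρ) = 0.36 × 66/2 = 11.88; df 1, 20 | 90.6% at 22 (89.1% at 21) |
| d = 0.6, so f = 0.3, interaction, correlation 0.6 | λ = f²·3N/(1−ρ) = 0.09 × 66/0.4 = 14.85; df 2, 40 | 92.4% at 22 (89.4% at 20) |
| Within-group change, paired t-test | noncentrality 0.6√n | 32 patients; 76.5% at 22 |
| Two-group difference, d = 0.6, t-test | noncentrality 0.6√(n/2) per arm | 60 per arm, 120 in total |
| Between-group difference of 0.6 SD of change, interaction | λ = (22/4) × (2/3) × 2 × 0.36 = 2.64; df 2, 40 | 27% at 22 |

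Three readings give 22 and three do not. The first needs no correlation and uses the test that section 2.8 plans.

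**2. Attrition.** 24 × 0.9 = 21.6, and 22/0.9 = 24.4, which rounds up to 25. The gap is one patient. At 21 patients the first reading still has 89.9%.

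**3. FMA on the planned interaction test.** Let SDc be the SD of change, D the between-group difference in change, and k the sum of squared deviations of the group differences over the three times, in units of D². Under sphericity the error variance σ²(1−ρ) equals SDc²/2, so the correlation cancels:

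λ = (N/4) · k · 2 · (D/SDc)², df 2 and 2(N−2).

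Differences (0, D, D) give k = 4/9 + 1/9 + 1/9 = 2/3. Differences (0, D, D/2) give k = 1/4 + 1/4 + 0 = 1/2.

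Example: N = 24, D = 5.2, SDc = 4, k = 2/3 gives λ = 6 × (2/3) × 2 × 1.69 = 13.52 and power 89.9%.

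| Assumed SDc (points) | 4 | 5 | 6 | 8 | 10 |
|---|---|---|---|---|---|
| N = 24, difference held | 90% | 72% | 55% | 34% | 23% |
| N = 24, halved by week 12 | 79% | 59% | 43% | 26% | 18% |
| N = 22, difference held | 87% | 68% | 51% | 31% | 21% |

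The break-even SDc for 90% power at 24 patients is 3.99 points (held) or 3.46 (halved). Both require the same SD of change at the two follow-ups. A simulation with assumed SDs of 4 at week 2 and 6 at week 12, correlation 0.6, gave about 71%.

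**4. What the table can show.** The SDs are assumed, and treating 5.2 points as a between-group target is a choice made here; section 2.6.1.1 quotes it only as an important difference. The table maps possibilities and does not estimate this trial's power.

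**The case for a change.** The case for acting is that the remedy is cheap: name the side, time point, effect-size type, contrast and test; say that FMA was not used for sizing; give FMA power conditional on an SD; and report the FMA difference with its 95% confidence interval beside 5.2 points. Several incompatible routes lead to 22, so a reader cannot tell what the 90% refers to, and over the assumed SDs FMA power runs from 90% down to 23%.

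Part of this stands. Section 2.2.2 is thinly documented, and its 0.6 cannot be checked from the text. A fuller paragraph would be better reporting.

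The rest does not carry a change. Section 2.2.2 says openly that it used one of the primary outcomes, so it does not offer the 90% as cover for FMA. An added FMA power sentence would rest on an SD the documents do not contain, and on sphericity and a sustained difference, so it could be as hard to rely on as the gap it fills. It would not help to read a non-significant result either; the estimated difference and its precision do that, and both follow from the change-score comparisons already planned in section 2.8. Sizing on FMA would need about 54 patients at an SD of 6 or 92 at 8. That is not a realistic alternative for a single-hospital study, described in the past tense, that screened from November 2015 to December 2016.

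**Conclusion.** No change follows. The gap is one of documentation: the 0.6 is under-described, and FMA has no power statement. No stated figure is shown to be wrong. The 22 reproduces at 91.5% on the planned test if 0.6 is Cohen's f from partial eta-squared, and on two further readings that need an unstated correlation; readings that give 32 or 120 remain possible but are not established. The one-patient difference in the attrition step is trivial.

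FMA power is unknown rather than shown to be low. It reaches 90% for 5.2 points with 24 analysed patients only if the SD of change is about 4.0 points or less, equal at both follow-ups, with the difference sustained (about 3.5 if it halves by week 12). Filling in the missing wording would alter neither the number enrolled, nor the tests, nor how the results are read. An analyst would sensibly interpret a non-significant FMA result through the estimated difference and its interval, without taking the MEP-based 90% as assurance for FMA. A sourced SD of FMA change well above 4 points would show low FMA power on these assumptions, but still no error in the MEP-based figure.

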## 2.3 Randomization and allocation concealment

The recruited individuals were randomly assigned to either the experimental group or the sham group by drawing a pre-set sealed opaque envelope. The group allocation was determined by the results of a randomized table set with  $4 \times 6$  blocks with an allocation ratio of 1:1. The results were printed and placed in separate envelopes. The envelopes were then numbered and put in sequence. Once the individual was recruited, he or she was assigned the next envelope in the sequence. The randomization was done by a researcher who was not involved in the outcome assessments.

The details of the clinical trial were explained to the potential participants by the investigators, and written informed consent was obtained before the commencement of data collection (Appendix I, II, III and IV). This trial protocol was approved by the Research Ethics Committee (Kowloon Central/Kowloon East) of the Hospital Authority (Appendix V), and the Human Research Ethics Subcommittee of the Hong Kong Polytechnic University (Appendix VI).

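### The 24 patients do not cover 10% attrition from 22 (a slip of 1 to 2 patients), and the 90% power at 22 cannot be checked because the meaning of the 0.6 effect size is not stated

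*Combined protocol and SAP*

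**What the plan says.** Section 2.2.2 (Sample size estimation) bases the calculation on motor-evoked potential (MEP), one of the primary outcomes. It cites a 20-person study in which "a significant improvement in MEP was shown in the intervention group". It continues: "The estimated effect size was about 0.6". "with the power set at 90" per cent and p < 0.05, it says "the minimum estimated sample size would be 22". The attrition step follows: "When considering a 10% attrition rate, the minimum sample size required would be 24 individuals with stroke".

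The section gives no effect-size metric, test, sidedness or correlation between visits. Other parts of the plan bear on the calculation:

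- Section 2.3 randomises in 4 × 6 blocks "with an allocation ratio of 1:1".
- Section 2.5.1 sets three assessments.
- Section 2.8 defines the treatment effect as the group by time interaction in a 2 × 3 mixed ANOVA. On significance levels it says: "The alpha was set at 0.05, except for post-hoc tests where the alpha was adjusted to 0.025".

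**The concern.** There are two separate problems in one short section.

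First, 22 is called a minimum and 10% is the stated loss, yet 24 less 10% is below 22. The plan's own figures disagree, though by little.

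Second, 22 in total is far smaller than a standardised between-arm difference of 0.6 would ordinarily need. It can be right under some other meaning of 0.6, but the reader is not told which. The source study is described by an improvement in its intervention group, which leaves open whether 0.6 is a within-group change or a difference between arms.

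This is the trial's only sample-size justification. A reader faced with a null result will lean on the 90%, and that figure may or may not apply to the test that section 2.8 plans.

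**Working it through.** **Inputs.** From section 2.2.2: effect size 0.6, power 90%, alpha 0.05, 22 patients before attrition, 10% attrition, 24 after. From section 2.3: two arms, 1:1. From sections 2.5.1 and 2.8: three visits, group by time interaction. Assumed because not stated: two-sided tests, sphericity, and visit correlations ρ over a range.

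**Attrition step**

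- Inflation by division: 22 / (1 − 0.10) = 24.4, so 25, or 26 for equal arms.
- Cruder inflation: 22 × 1.10 = 24.2, which also rounds up to 25.
- Check on the stated figure: 24 × 0.90 = 21.6, below 22.
- What 24 does cover: (24 − 22) / 24 = 2/24 = 8.3%.

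The 24 is therefore reached only by rounding a minimum down.

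**Can 22 be reproduced?** Yes, by at least three routes. Each needs something the plan does not state. In the repeated-measures routes, N is the total number of patients and m = 3 visits.

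1. Group by time interaction with f = 0.3 (taking f = d/2 = 0.6/2): noncentrality λ = N f² m / (1 − ρ), with 2 and 2(N − 2) degrees of freedom. At N = 22 and ρ = 0.57, λ = 22 × 0.09 × 3 / 0.43 = 13.8 on 2 and 40 df, and power is 0.903. At ρ = 0.56 it is 0.896.
2. Group main effect with f = 0.6: λ = N f² m / (1 + (m − 1)ρ), with 1 and N − 2 df. At N = 22 and ρ = 0.5, λ = 22 × 0.36 × 3 / 2 = 11.9 and power is 0.906. At N = 20 it is 0.874, so 22 is exactly the minimum with equal arms.
3. 0.6 read as a correlation r: d = 2r / √(1 − r²) = 1.2 / 0.8 = 1.5. A two-sample t-test at 11 per arm has power 0.917, and at 10 per arm 0.887. Again 22 is the minimum, with no repeated measures involved.

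**Readings on which 22 does not give 90%**

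| Meaning of 0.6 | Test | Power at 22 | Total N for 90% |
|---|---|---|---|
| Between-arm Cohen's d | Two-sample t, 11 per arm; noncentrality 0.6 × √(11/2) = 1.41 | 27% | 120 (60 per arm) |
| Within-person effect, all 22 patients | Paired t; noncentrality 0.6 × √22 = 2.81 | 77% | 32 |

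One-sided versions of these two tests need 98 and 26, so sidedness alone does not account for 22.

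**Planned interaction, f = 0.3, three visits**

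| Visit correlation | λ at 22 | Power at 22 | Power at 24 |
|---|---|---|---|
| 0.3 | 8.5 | 71% | 75% |
| 0.5 | 11.9 | 85% | 89% |
| 0.7 | 19.8 | 98% | 99% |

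The λ column is 22 × 0.09 × 3 = 5.94 divided by 0.7, 0.5 and 0.3. The column for 24 uses the same formula with 24 × 0.09 × 3 = 6.48 and 2 and 44 df.

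**The case against.** **The attrition gap is trivial.** Expected completers fall short by 22 − 21.6 = 0.4 of a patient. That is fair as to size. One could add that, with independent 10% loss, the chance of keeping at least 22 is only 56% from 24 (76% from 25, 89% from 26). But the plan never promises a completer count. Section 2.8 also runs the intention-to-treat analysis first, with last observation carried forward, so patients lost after baseline stay in that analysis. The 56% should not be pressed. The arithmetic slip remains.

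**Enrolling 26 would not fit the randomisation.** The product of 4 and 6 is 24, and 26 is a multiple of neither. This counts against treating 26 as the required remedy. It does not make 24 a 10% allowance.

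**The low power figures rest on a reading the plan does not adopt.** This stands. The 27% assumes that 0.6 is Cohen's d tested by a single two-sample t-test. Section 2.8 instead plans a repeated-measures interaction and uses independent t-tests on change scores only post hoc. A reader might infer that the trial has 27% power, or that 22 arises under one particular repeated-measures assumption and no other. Neither is supported. Three routes give 22, one of them without repeated measures, and the documents do not say which, if any, was used.

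Those routes do not settle the matter in the plan's favour either. The group main effect with f = 0.6 corresponds to d = 2 × 0.6 = 1.2, and r = 0.6 to d = 1.5, at least double the ordinary reading. The main effect is also a different test from the interaction that section 2.8 calls the treatment effect.

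**Conclusion.** The concern holds in two limited parts.

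- **Attrition.** The stated 24 is wrong as written for 10% loss from 22, by 1 patient (25) or 2 (26 for equal arms). This follows from the plan's own numbers and needs no assumption.
- **Power.** The 90% at 22 cannot be verified. It depends on an unstated metric and, in the repeated-measures routes, on an unstated visit correlation. Across the readings tried, power at 22 runs from 27% to 98%. For the planned interaction with f = 0.3 it runs from 71% to 98% at correlations of 0.3 to 0.7, and reaches 90% near 0.57. These figures assume two-sided 0.05 and, for the interaction, sphericity and f = d/2.

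The documents do not support saying that 90% is wrong or that more patients had to be enrolled. The meaning of 0.6 rests on a cited study that is not part of the documents.

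**What to change.** Make two changes to section 2.2.2, both text only and with no added enrolment:

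1. State that 24 allows for the loss of 2 patients (8.3%), in place of 10%.
2. State what the 0.6 is (d, paired effect, f or r; within-group or between-arm), and the test and sidedness behind the 22. Replace the bare 90% with the power that 22 completers, or 24 patients, give for the group by time interaction of section 2.8, over a range of visit correlations such as 0.3 to 0.7.

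The cost is in how the plan reads. The stated attrition allowance becomes less favourable, and the stated power possibly does too. If 0.6 turns out to be f for the group main effect (with ρ = 0.5) or r, 24 patients give 93% or 94% for that comparison. In the main-effect case, the power for the interaction would still have to be given.
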